## STOP-BANG Sleep Apnea Questionnaire

Name \_\_\_\_\_ Height \_\_\_\_\_ Weight \_\_\_\_\_

Age \_\_\_\_\_ Male / Female \_\_\_\_\_

STOP			
Do you SNORE loudly (louder than talking or loud (enough to be heard through closed doors)?	Yes	No	
Do you often feel TIRED, fatigued, or sleepy during daytime?	Yes	No	
Has anyone OBSERVED you stop breathing during your sleep?	Yes	No	
Do you have or are you being treated for high blood PRESSURE?	Yes	No	
BANG			
BMI more than 35kg/m  ?	Yes	No	
AGE over 50 years old?	Yes	No	
NECK circumference > 16 inches (40cm)?	Yes	No	
GENDER: Male?	Yes	No	
TOTAL SCORE			

**High risk of OSA: Yes 5 – 8**

**Intermediate risk of OSA: Yes 3 - 4**

**Low risk of OSA: Yes 0 - 2**

Official title: Napping, Sleep, Cognitive Decline and Risk of Alzheimer's Disease

NCT#: NCT03256539

Document date: 09/21/2023

SleepTIGHT Statistical Analysis Plan

(Sleep Therapeutics Intervention to improve coGnitive HealTh)

***Full Study Title: Napping, Sleep, Cognitive Decline and Risk of
Alzheimer's Disease***

Principal Investigator: [name]

University of California, San Francisco

[name]

[name]

[contact]

Sponsor

National Institutes of Health

STUDY AIMS

The overall objective is to develop a CBT-I program for people with MCI/ mild Alzheimer's disease and sleep disturbances, pilot test its feasibility, and elucidate its preliminary effects on sleep, cognition and quality of life, with the ultimate aim of decreasing risk of Alzheimer's onset or progression.

Aim 1: To develop a CBT-I program and test its feasibility and acceptability in patients with MCI/ mild Alzheimer's disease and sleep disturbances.

Aim 2: To elucidate the effects of the CBT-I program on patients' subjective and objective sleep quality.

Exploratory Aim: To collect pilot data and explore preliminary effects of 1) the CBT-I program on cognition and quality of life and 2) involving caregivers in the program.

PROCEDURES

We plan to study older adults (aged 65 and above) with MCI or mild AD. Patients will be identified from a combination of online sources, including the UCSF CTSI Electronic Health Record services (MyChart), Researchmatch.org and social media postings, as well as the UCSF Memory and Aging Center (MAC, Director: [name], co-founders include [name]). *The attached figure* outlines the study visits and related measurements.

1. Baseline screening/ Randomization

When a potential participant is identified or expresses interest in the study, study staff will contact them to explain study procedures and go through the key points of the consent form. Once consented, study staff will administer clinical interviews via zoom to assess insomnia, medical history, mood and QDRS-derived global CDR to determine eligibility and obtain visual proof of written informed consent. Eligible participants who consent will be scheduled for a baseline assessment via zoom within 2 weeks of enrollment. The measures described above will also serve as part of the baseline measures.

Baseline Visit: At the baseline zoom visit, study staff will administer detailed assessment of sleep quality, quality of life and cognitive function, using the Pittsburgh Sleep Quality Index (PSQI) (general sleep quality), Epworth Sleepiness Scale (excessive daytime sleepiness), the 36-Item Short Form Survey (SF-36) (quality of life) and a standardized battery of neurocognitive tests selected for their sensitivity in evaluating multiple potentially relevant cognitive domains, feasibility of administration during either in-person or telehealth visits, and manageable burden to participants and study personnel in the setting of a full-scale randomized trial. In addition, study staff will give detailed instructions on the use of sleep assessment device (Actiwatch Spectrum® from Philips Respiration, Inc for the measure of 24-h sleep-wake activities) and the corresponding sleep diary (questions such as bed time, wake time, nap times, and any times when watch is removed and for what reason).

2. Intervention (9 weeks). We will randomize patients, using computer-generated random numbers, to one of two treatment arms: a) an FDA-authorized prescription digital CBT-I therapeutic called the Somryst or b) an interactive, attention-matched, internet-based placebo control program. At the beginning of the intervention, study staff will give instructions on the use of the programs via zoom. Throughout the intervention, study staff will call the participants weekly to give further clarifications and answer questions. Somryst is a 9-week program that delivers digital CBT-I therapeutic content, and can be used on a mobile device, such as a smartphone or tablet. CBT-I is a neurobehavioral treatment which focuses on addressing the maladaptive behaviors, routines, and dysfunctional thoughts that perpetuate sleep problems, regardless of the cause of sleep problems. CBT-I is typically delivered by a specialty-trained clinician, either 1:1 or in group format. Standard delivery of CBT-I usually occurs in weekly sessions over 6-8 weeks. CBT-I can be conceptualized as six sessions or cores that deliver proven behavioral and cognitive treatment strategies. The Somryst program is intended to deliver 6 treatment Cores, with the following specific CBT-I therapy content: 1. Get Ready: This Core sets the stage for the therapeutic experience. It lets the participant know what they will need to learn and do to improve sleep and sets goals for success. 2. Sleep Window: This Core focuses on the concept of sleep restriction and identifies a Sleep Window - a recommended Bedtime and Arising Time – the participant should follow. 3. Behaviors: This Core focuses on stimulus control and establishes guidelines for participants to follow while implementing their Sleep Window. 4. Thoughts: This Core explains how a participant's thinking can contribute to insomnia. The participant will learn to identify, and shift thought patterns. 5. Education: This Core helps the participant identify changes to be made in their lifestyle and environment that can promote better sleep. 6. Looking Ahead: This Core pulls together what the participant has learned, prepares the participant for the future, and teaches them what to do if they experience a relapse. Somryst also includes a daily Sleep Diary in which the participant records information about their sleep.

3 Follow-up and outcome measures. The primary goal of this research is to pilot test the feasibility of implementing this CBT-I program in patients with MCI or mild AD. Following the last session of CBT-I, participants will be asked to report their satisfaction and acceptability of the treatment. We will also assess eligibility, consent, and retention rates, as well as data quality and completeness. To explore the initial effects of this treatment on sleep and cognition, we will repeat baseline measurements, including the neuropsychological battery and the questionnaires (ISI, PSQI, ESS and SF-36) towards the end of the intervention.

STATISTICAL ANALYSES

To assess the randomization, baseline demographic and clinical characteristics will be compared between arms using parametric (e.g. t-test) or nonparametric test (e.g. chi-square, Wilcoxon tests); variables that are not balanced across treatment arms will be adjusted for in subsequent analyses. The primary analysis will use the intent-to-treat principle. Secondary subgroup analyses will assess the role of treatment adherence on outcomes, using measures of compliance applicable to both study arms, thus avoiding the well-known biases of a “compliers only” analysis.

For Aim 2 and the Exploratory Aim, we will use t-tests, Wilcoxon or chi-square tests to compare between the treatment and non-treatment groups the change scores in: 1) circadian rhythms parameters (e.g. amplitude, and overall rhythmicity); 2) frequency and length of day naps; 3) quality of nocturnal sleep (e.g. change in ISI scores; increased sleep duration and efficiency; decreased sleep onset time); 4) reported quality of life (SF-36 scores); 5) cognitive scores. Standardized measures of cognitive performance (z-scores) will be calculated for each participant for each neuropsychological test in the battery. Repeated measures models will be used to examine longitudinal treatment effects. These models will include subject-specific (i.e. intercept term) and fixed effects (treatment group, time and the time*treatment interaction). A significant time*treatment interaction will indicate that changes in outcome measures over time are different in the treatment arms. In order to explore the impact of involvement of caregivers, we will repeat the above analysis between the treatment group with and without involvement of the caregiver. The resulting estimates will be imprecise, and thus useful for trial planning only in combination with external data, expert opinion, and established norms for clinically meaningful effects.

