Diagnosis and Main Inclusion Criteria	
Inclusion Criteria
 
 
• 1) Age 65+,
 
• 2) evidence of MCI, defined as: self-reported quick dementia rating system (QDRS) - derived global clinical dementia rating score of .5,
 
• 3) adequate visual and auditory acuity to allow neuropsychological testing;
 
• 4) evidence of subthreshold or clinical insomnia, defined as a score of 8 or more on the insomnia severity index,
 
• 5) ability to speak understand and write in English, 6) study partner willing to participate,
 
• 7) capacity to give written informed consent; and
 
• 8) owns one or more smartphone or tablet devices that can be used to access the internet and to participate in video conferences.
 
 
Exclusion Criteria
 
 
• 1) Self-reported diagnosis by a physician of any major neurologic disease such as Alzheimer's disease, other dementia, Parkinson's disease, multiple sclerosis, epilepsy, Huntington's disease;
 
• 2) History of brain tumor or significant head trauma (loss of consciousness >30 minutes);
 
• 3) Evidence (CT or MRI scans within 12 months prior to screening) of brain infarction or other focal lesions; 4) Any comorbid psychiatric conditions or severe personality disorder within the past 2 years (by DSM-V), such as major depression, bipolar disorder, schizophrenia, and other psychotic features;
 
• 5) Any uncontrolled medical conditions or systemic illness that might lead to difficulty complying with the study protocol;
 
• 6) Any concomitant treatment that might confound the results (participants must be off all psychotropic medications, including hypnotic medications, and non-pharmacological treatments, for at least 30 days prior to screening);
 
• 7) History of alcohol or substance abuse within the past 2 years;
 
• 8) Shift workers; and
 
• 9) Any inadequately treated primary or secondary sleep disorders
 

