## Study Schedule & Procedure Summary

### SCHEDULE OF EVALUATIONS

ASSESSMENT	Recruitment Pre-screening & Consent	Screening/ Assessment	Baseline Measures/ Start of Trial	9 Weeks/ End of Trial Follow-up
Inclusion/Exclusion Criteria	X			
Medical History	X	X		
Insomnia Severity Index	X	X		X
Pittsburg Sleep Quality Index		X		X
SF-36			X	X
Epworth Sleepiness Scale			X	X
Quality of Life			X	X
Cognitive function			X	X
Geriatric Depression Scale			X	
24-h Actigraphy (3 days)			X	X
Cognitive Assessment Battery			X	X

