### INITIAL CONTACT AND SCREENING

1. Participants, after being identified or reaching out to research team with interest, will be called with initial **contact phone script**, given introductory information about the study, asked to confirm their interest and given the option to fill **consent form** on same call or to schedule follow-up call for consent. IF participant is still interested, consent form is signed, then **ISI questionnaire** is given.

2. Followed by appointment for:

- Baseline Cognitive Assessment Interview: 1 hour via Zoom.
- Administer the following questionnaires:
  - **Pittsburg Sleep quality index**
  - **Epworth Sleepiness Scale**
  - **36-item short-form survey**

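### The protocol schedules two pre-randomisation ISI scores, but the SAP does not say which is the baseline and compares ISI change without planned baseline adjustment, leaving some precision unused

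*SAP*

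**What the plan says.** Entry requires "evidence of subthreshold or clinical insomnia, defined as a score of 8 or more on the insomnia severity index" (Protocol, Diagnosis and Main Inclusion Criteria).

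In the protocol's Schedule of Evaluations, the row "Insomnia Severity Index" is marked under pre-screening and consent, under screening/assessment, and at 9 weeks. It is not marked under baseline measures. The protocol's Initial Contact and Screening section describes one early administration only: "consent form is signed, then ISI questionnaire is given". Its list for the next appointment has the PSQI, Epworth scale and SF-36, but not the ISI.

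The SAP (Procedures, 1. Baseline screening/ Randomization) says "study staff will administer clinical interviews via zoom to assess insomnia, medical history, mood and QDRS-derived global CDR to determine eligibility", and then "The measures described above will also serve as part of the baseline measures". Its Baseline Visit paragraph opens "At the baseline zoom visit, study staff will administer detailed assessment of sleep quality, quality of life and cognitive function" and names instruments without the ISI. Its follow-up section nevertheless lists the ISI among the baseline questionnaires to be repeated towards the end of the intervention.

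Under Statistical Analyses, "change in ISI scores" is an example of a sleep outcome compared between arms by t-test or Wilcoxon test on change scores. A repeated-measures model with a time-by-treatment term is also planned.

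**The concern.** Taken together, these places give an ISI baseline that comes from screening, where a threshold of 8 applies, and possibly two such scores with no rule for using them. Two things follow.

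First, precision. If two scores exist before randomisation, a comparison that uses one of them as the subtracted baseline is noisier than it need be. In a 40-person trial that matters somewhat. With no rule, the choice of baseline could also be made after the data are seen.

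Second, interpretation. A score selected for being 8 or more lies, on average, above the person's usual level and falls back without treatment. The fall is the same in expectation in both arms. It therefore leaves the arm contrast unbiased, but it enters any within-arm change and the time effect of the repeated-measures model.

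**Working it through.** **Inputs from the documents:** entry at ISI of 8 or more; 40 participants; ISI marked twice before the start of trial and once at 9 weeks (schedule table). The documents give no ISI standard deviation, correlation, power or allocation ratio, so there is no stated figure to reproduce.

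**Assumptions:** equal SD at each time; rf = correlation of a pre-randomisation score with week 9; rb = correlation of the two pre-randomisation scores; 20 per arm.

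**Variance of the arm comparison, in units of SD², before truncation**

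- Change from one score: 2(1 − rf)
- Change from the mean of two: 1 + (1 + rb)/2 − 2rf
- ANCOVA on one score: 1 − rf²
- ANCOVA on the mean of two: 1 − 2rf²/(1 + rb)

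| rf | rb | Change, one | Change, mean of two | Cut | ANCOVA, one | ANCOVA, mean of two | Cut |
|---|---|---|---|---|---|---|---|
| 0.5 | 0.5 | 1.00 | 0.75 | 25% | 0.750 | 0.667 | 11% |
| 0.5 | 0.7 | 1.00 | 0.85 | 15% | 0.750 | 0.706 | 6% |
| 0.5 | 0.9 | 1.00 | 0.95 | 5% | 0.750 | 0.737 | 2% |
| 0.6 | 0.6 | 0.80 | 0.60 | 25% | 0.640 | 0.550 | 14% |
| 0.7 | 0.7 | 0.60 | 0.45 | 25% | 0.510 | 0.424 | 17% |
| 0.7 | 0.9 | 0.60 | 0.55 | 8% | 0.510 | 0.484 | 5% |

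ANCOVA on a single score already improves on the change score by 1 − (1 + rf)/2, which is 25%, 20% and 15% at rf 0.5, 0.6 and 0.7.

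**With entry truncated at 8** (simulation, 400,000 draws per scenario, screened mean 8-14, SD 4-6, rf 0.5 or 0.7): the change-score cut is about 16-23% when rb = rf and about 2-8% when rb = 0.9.

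**What that means at 20 per arm** (no truncation). The 80%-power, two-sided 5% detectable difference is 0.909 × SD of change. With an assumed ISI SD of 5:

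- rf = rb = 0.6: 0.909 × 5 × √0.80 = 4.07 points, falling to 0.909 × 5 × √0.60 = 3.52.
- rf = 0.5, rb = 0.9: 0.909 × 5 × √1.00 = 4.55 points, falling to 0.909 × 5 × √0.95 = 4.43.

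**Regression to the mean within an arm:** SD(1 − rf) × φ(c)/(1 − Φ(c)), with c = (7.5 − mean)/SD.

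- Mean 11, SD 5, rf 0.5: c = −0.70, φ/(1 − Φ) = 0.3123/0.7580 = 0.412, so 5 × 0.5 × 0.412 = 1.03 points.
- Over mean 8-14, SD 4-6 and rf 0.5-0.7 the formula runs from 0.13 to 2.24. Simulation agrees, and reaches 2.35 if both scores must be 8 or more. The range is roughly 0.1-2.3 points.
- By arm at mean 11, SD 5, rf 0.5, simulation gives 1.02 and 1.03 points, so the contrast is unaffected.

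**Does a second score as within-arm baseline cure this?** If only the first score is thresholded, the share remaining is (rb − rf)/(1 − rf). At rf 0.5 this is 0 for rb 0.5, (0.7 − 0.5)/0.5 = 40% for rb 0.7, and (0.9 − 0.5)/0.5 = 80% for rb 0.9. If both scores are thresholded, averaging them does not reduce it: at mean 11, SD 5 and rf = rb = 0.5 it is about 0.8 points with either baseline.

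**The case against.** Several stronger readings are tempting, and the documents do not support them.

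- *One score admits the participant and the other is thrown away.* Neither document says which score admits, whether the threshold applies to both, or that either is discarded. The SAP's eligibility sentence speaks of insomnia and does not name the ISI. The link to the ISI comes from the inclusion criterion and from the absence of any other ISI baseline in the SAP. The repeated-measures paragraph does not say which ISI time points enter.
- *Two scores are certainly available.* The second rests on the schedule table alone; the written procedure gives one.
- *The plan will report an inflated improvement.* No within-arm test is specified. The planned inference is between arms, and the SAP says its estimates serve trial planning only alongside external data.
- *The gain is 25%.* That needs two scores taken close together to correlate no better than either does with week 9. The ISI asks about the last 2 weeks and the SAP books the baseline visit within 2 weeks of enrollment, so the recall periods may overlap and rb may be high.

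It is also fair to say that a single pre-randomisation baseline is valid, that the SAP would adjust for baseline variables found to be unbalanced, and that it concedes imprecision. All of this stands and limits the point. It does not remove it. Adjustment triggered by observed imbalance is not a prespecified baseline adjustment, and conceding imprecision is no reason to leave scheduled data unused.

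**Conclusion.** The point holds as a low-cost improvement in precision and a needed clarification. It is not a validity error: the between-arm comparison of ISI change is unbiased as planned.

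The sizes in the brief depend wholly on assumed correlations, standard deviations and screened means, and the ANCOVA figures ignore truncation. The lower end of the precision range is plausible given the timing of the two scores. If only one score is in fact taken, nothing is gained by averaging, but baseline adjustment still helps. The regression-to-the-mean figure bears only on within-arm change or the time effect.

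The consequence for the trial is small, because its primary outcomes are feasibility and acceptability and ISI change is one of many Aim 2 measures.

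**What to change.** 1. In the SAP, compare week-9 ISI between arms by ANCOVA, with the mean of the available pre-randomisation ISI scores as covariate, and the single score where only one exists.
2. Reconcile the protocol's Schedule of Evaluations, its Initial Contact and Screening section and the SAP's Baseline screening/ Randomization section on how many ISI scores are taken before randomisation and which one the threshold of 8 applies to.
3. State that within-arm ISI change is not to be read as a treatment effect. If it is described, a non-qualifying second score as its baseline reduces regression to the mean but does not generally remove it.

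The cost is two or three sentences in the SAP and an alignment of the protocol text. If the schedule table reflects practice, there is no added burden on participants.

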## B. FOLLOW-UP MEASURES

Once intervention is completed,

- Feedback at the end of trial via survey and phone follow-up (if needed)
- Follow-up (3-day actigraphy & questionnaires + Cognitive Assessments)
- Follow-up at 24 weeks:
- Final follow-up actigraphy watch measurement
- Follow-up of cognitive assessment + questionnaires

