## OUTCOME MEASURES

Primary Outcomes

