### Feasibility

Proportion of eligible participants consented

- Proportion of participants randomized after baseline assessment
- Number of CBT-I sessions completed
- Adherence/compliance rates
- Follow-up rates
- Missing data (data completeness)
- Time needed to collect and analyze data

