### Acceptability

General study satisfaction

Acceptability of intervention

Barriers & Burden

[figure not shown]
Qualitative interview

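### Satisfaction and acceptability are primary outcomes but are asked for only once the program is finished, with no written assessment for people who stop early, so the figure is likely to be too favourable

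*SAP*

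**What the plan says.** Protocol, Outcome Measures: under "Primary Outcomes" there are two groups, Feasibility and Acceptability. The Acceptability group contains "General study satisfaction", "Acceptability of intervention", barriers and burden, and "Qualitative interview". No instrument, threshold, time point or denominator is given for any of them. Aim 1 of the SAP names acceptability alongside feasibility.

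The documents time the collection in two places:

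- SAP, section 3 (Follow-up and outcome measures): "Following the last session of CBT-I, participants will be asked to report their satisfaction and acceptability of the treatment".
- Protocol, B. Follow-up Measures: "Feedback at the end of trial via survey and phone follow-up (if needed". This comes under a lead-in that presupposes the intervention is complete. No arm is named.

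The Schedule of Evaluations has a column for the 9-week end-of-trial follow-up, but no row for satisfaction, acceptability, feedback or interview. The protocol section on withdrawal lets participants stop whenever they wish and lets the study doctor remove them. It describes no exit survey or interview.

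**The concern.** Acceptability is meant to show whether people with MCI can tolerate this program. Those best placed to report that it was too hard or too burdensome are the ones who stop. If the question is put only to those who reach the last session, the answers come from a group selected for having coped.

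This also sits badly with the SAP's own standard. Its Statistical Analyses section adopts intent-to-treat for the primary analysis and, when it describes the adherence analyses, warns against the bias of looking at compliers alone. A collection rule tied to completion brings the same selection into a primary outcome before any analysis starts. Answers not sought when someone stops may not be recoverable later.

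A second matter is the control arm. Without its answers, satisfaction with the CBT-I content cannot be told apart from satisfaction with the video meetings and weekly calls, which is a comparison the attention-matched program could support.

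**Working it through.** The plan has no figure to reproduce. It gives 40 subjects, but no allocation ratio, expected dropout, acceptability threshold or rule for missing acceptability data.

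**Step 1: whom each text reaches**

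| Text | Trigger | Finishes CBT-I | Stops CBT-I early | Control arm |
|---|---|---|---|---|
| SAP, section 3 | last CBT-I session | asked | not asked, if read literally | has no CBT-I session |
| Protocol, B. Follow-up Measures | end of trial, after a completed intervention | asked | unclear | not excluded |
| Protocol, Appendix A, Brief Study Overview | none stated | told to expect questionnaires on their experience | same | same |
| Protocol, Schedule of Evaluations | week-9 column, no row | silent | silent | silent |
| Protocol, withdrawal section | none | not applicable | no exit assessment | no exit assessment |

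No text clearly reaches the early stopper. The control arm is reached on one reading of the protocol, but not by the SAP sentence.

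The last session is also not a fixed date. The protocol describes six weeks of intervention in its procedure summary and section A, while its Description of the Intervention and the SAP give nine. Those passages need to be reconciled.

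**Step 2: direction and size of the error**

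Let d be the share who stop early, s_c the share satisfied among finishers, and s_d the share satisfied among those who stop.

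- Value among all randomised = (1 − d) × s_c + d × s_d
- Finishers-only value = s_c
- Overstatement = d × (s_c − s_d)

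Assumed ranges, not from the documents: s_c from 80% to 90% and s_d from 20% to 50%. The gap s_c − s_d then runs from 80 − 50 = 30 to 90 − 20 = 70 points.

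| d | Smallest overstatement | Largest overstatement |
|---|---|---|
| 10% | 0.10 × 30 = 3 points | 0.10 × 70 = 7 points |
| 20% | 0.20 × 30 = 6 | 0.20 × 70 = 14 |
| 30% | 0.30 × 30 = 9 | 0.30 × 70 = 21 |
| 40% | 0.40 × 30 = 12 | 0.40 × 70 = 28 |

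The overstatement is zero if nobody stops or if s_d = s_c. It is negative if those who stop are more satisfied than those who finish.

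**Step 3: in participants**

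Assume 1:1 allocation, so 40/2 = 20 in the CBT-I arm, with 14 finishing and 12 of those satisfied.

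- Finishers only: 12/14 = 85.7%
- None of the 6 others satisfied: 12/20 = 60%
- Two of the 6 satisfied: 14/20 = 70%
- Five of the 6 satisfied: 17/20 = 85%
- All 6 satisfied: 18/20 = 90%

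In this example the finishers-only figure is too high unless all six non-finishers are satisfied.

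With 10 of 20 finishing and 9 of those satisfied, the finishers-only figure is 9/10 = 90%, against bounds of 9/20 = 45% and 19/20 = 95%.

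**The case against.** The strongest reply is that the protocol's survey is placed at the end of the trial and the schedule has a week-9 column. Someone who stops the program but stays in the study could therefore still be surveyed. That is a fair reading, but the lead-in about a completed intervention cuts against it, the SAP sentence contradicts it, and it does nothing for people who leave the study.

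The missing schedule row is weak evidence by itself. The same table also omits the QDRS, the sleep diary and the 24-week visit, all planned elsewhere. The study outline figure, and a figure within the Acceptability list, are not visible, so a feedback step there cannot be excluded. Barriers, burden and the interview have no stated timing at all, and staff phone participants weekly, although the stated purpose is to clarify and answer questions.

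Retention, follow-up and data completeness are reported separately, so a reader would see how many were lost. This shows the gap but does not correct the acceptability figure.

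Three stronger readings are tempting and are not supported:

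- *The control arm has no acceptability assessment.* The protocol's survey names no arm, satisfaction with the study as a whole is listed, and the phone script tells every candidate, before randomisation, to expect questionnaires on their experience. Control-arm collection is unclear, not absent.
- *The figure is bound to be too favourable.* The bounds above include values higher than the finishers-only figure. Likely is as far as the evidence goes.
- *The primary count "Number of CBT-I sessions completed" conflicts with the SAP's adherence analysis.* It is a natural feasibility count for the CBT-I program. Adherence is a separate item in the same list, and the SAP already commits to "using measures of compliance applicable to both study arms". No change is needed there.

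**Conclusion.** The point holds in a limited form. A primary outcome is timed by completion in both documents, and nothing written ensures that early stoppers are asked. Followed literally, the rule gives a figure that leans towards finishers and is likely to be too favourable.

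On the assumed rates the overstatement is 3 to 28 points for dropout of 10% to 40%. This rests on assumed dropout, satisfaction and 1:1 allocation, and on the figure being computed among those asked, because the plan states no denominator. With about 20 people per arm, a handful of unasked participants could change how the result is read. The control-arm question is a mismatch of wording between SAP and protocol that should be settled. This is an inexpensive improvement worth making, and it does not invalidate the trial.

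**What to change.** 1. In SAP section 3, replace the trigger with: *The satisfaction and acceptability questions, including barriers and burden, are asked of every randomised participant in both arms at the 9-week end-of-trial visit, whether or not the program was finished, and at the time of stopping for anyone who leaves early.*
2. Add a matching row to the Schedule of Evaluations, marked at end of trial and at early stop, and align the lead-in in B. Follow-up Measures.
3. Report acceptability per arm with all randomised participants as the denominator. Show non-responders as their own category, including those who decline the exit questions, and give worst/best-case bounds as in the working.

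The cost is a few sentences, one table row and a short extra contact when someone stops. The survey and weekly staff calls are already planned. The reported acceptability will probably be lower. If collection has already closed, the third step can still be done.

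### The randomised Aim 2 and exploratory comparisons use change scores without prespecified baseline adjustment; adding it would usually sharpen the estimates at a small, bounded cost

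*SAP*

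**What the plan says.** The SAP's Statistical Analyses section sets out three relevant steps.

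- **Baseline tests and covariates.** "To assess the randomization, baseline demographic and clinical characteristics will be compared between arms" by parametric or nonparametric tests, and "variables that are not balanced across treatment arms will be adjusted for in subsequent analyses". No cut-off, covariate list or adjusted model is given. Nor does the section say how a t-test, Wilcoxon or chi-square test would be adjusted.
- **Outcome comparisons.** The sentence covering both Aim 2 and exploratory outcomes reads: "we will use t-tests, Wilcoxon or chi-square tests to compare between the treatment and non-treatment groups the change scores in". The outcomes then listed are circadian parameters, naps ("frequency and length of day naps"), nocturnal sleep, SF-36 and cognitive scores. Cognitive tests are first converted to z-scores.
- **Longitudinal model.** "These models will include subject-specific (i.e. intercept term) and fixed effects (treatment group, time and the time*treatment interaction". The baseline value is not listed as a covariate.

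On timing, the SAP's section on follow-up and outcome measures says "we will repeat baseline measurements, including the neuropsychological battery and the questionnaires (ISI, PSQI, ESS and SF-36) towards the end of the intervention". The protocol's Schedule of Evaluations places this at 9 weeks and includes actigraphy at baseline and at 9 weeks. The protocol's Follow-up Measures section adds a 24-week visit: "Follow-up of cognitive assessment + questionnaires".

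The SAP also limits what the results are for: "The resulting estimates will be imprecise, and thus useful for trial planning only in combination with external data".

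**The concern.** An outcome's baseline value usually predicts its follow-up value, and this trial collects it anyway. Subtracting baseline fixes the slope of follow-up on baseline at 1. A linear model with baseline as a covariate (ANCOVA) estimates that slope, and unless the true slope is close to 1 it gives a more precise arm difference. Under the plan, the outcome's own baseline enters as a covariate only if a chance imbalance happens to flag it, by a criterion that is not written down.

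Two things are at stake. One is the width of the intervals that are meant to feed the planning of a later trial. The other is whether the model is fixed before the data are seen. The feasibility and acceptability outcomes, which are primary, do not depend on either.

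**Working it through.** **Inputs.** The protocol synopsis gives 40 subjects, with no power calculation behind that number, so there is no sample-size figure to reproduce. Assumed, because the documents do not give them: 1:1 allocation (20 per arm), 16 per arm as a 20% loss scenario, the correlation ρ between baseline and follow-up, and the ratio k of follow-up SD to baseline SD.

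**1. Does the repeated-measures model already adjust?** With two complete visits, its time-by-treatment term is the difference in mean change. On a check dataset both methods gave 0.8086 with SE 0.3516; ANCOVA on the same data had SE 0.3121. So at week 9 the model does not supply the adjustment.

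**2. Variance ratio, ANCOVA to change score, n per arm:**

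k²(1 − ρ²) / (1 + k² − 2ρk) × (2n − 3)/(2n − 4)

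With k = 1 and n = 20 this is (1 + ρ)/2 × 37/36. The 95% half-widths, in SD units, are t(0.975, 38)·√[2(1 − ρ)·2/20] for change and t(0.975, 37)·√[(1 − ρ²)·(2/20)·37/36] for ANCOVA.

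| ρ | Ratio, n = 20 | Variance cut | Half-width, change → ANCOVA | Ratio, n = 16 |
|---|---|---|---|---|
| 0.3 | 0.668 | 33% | 0.757 → 0.620 | 0.673 |
| 0.5 | 0.771 | 23% | 0.640 → 0.563 | 0.777 |
| 0.7 | 0.874 | 13% | 0.496 → 0.464 | 0.880 |
| 0.9 | 0.976 | 2% | 0.286 → 0.283 | 0.984 |

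Simulation (200,000 trials per setting, n = 20) gave 0.669, 0.773, 0.872 and 0.977. At ρ = 0.5, 40 people analysed by ANCOVA are worth about 40/0.771 ≈ 52 analysed by change score.

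**3. Unequal SDs, n = 20.** k = 0.8, ρ = 0.5: ratio 0.587 (41% cut). k = 1.25, ρ = 0.5: 0.918 (8% cut). k = 1.25, ρ = 0.7: 1.008 (0.8% loss). k = 1.25, ρ = 0.8: 1.028 (2.8% loss).

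**4. Worst case.** In units of baseline variance, the change-score variance exceeds the ANCOVA residual variance by (1 − kρ)², which is never negative. The ratio therefore cannot exceed (2n − 3)/(2n − 4), and reaches it only when the slope kρ is exactly 1. With one covariate:

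- 20 per arm: 37/36 = 1.028, so 2.8% of variance and 1.5% of half-width.
- 16 per arm: 29/28 = 1.036, so 3.6% and 1.9%.
- Caregiver comparison, about 20 people in total: 17/16 = 1.0625, so about 6% and 3.5%.

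**5. ISI.** The inclusion criteria require an ISI of 8 or more, which truncates the baseline and shrinks its variance. Take a normal baseline with unit SD before truncation, slope 0.5 and residual variance 0.75. If the truncated variance is v, the ratio is 0.75 × (37/36) / (0.25v + 0.75).

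- Cut 1 SD below the mean: v = 0.630, ratio 0.85, a 15% cut.
- Cut at the mean: v = 0.363, ratio 0.92, an 8% cut.
- Cut 0.5 SD above the mean: v = 0.268, ratio 0.94, a 6% cut.

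These compare with 23% untruncated. The real position of the cut is unknown.

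**6. How much does the imbalance rule recover?** Suppose it is applied to the outcome's own baseline, with n = 20, k = 1 and ρ = 0.5. The variance relative to the plain change score is 0.940, 0.904, 0.855 and 0.824 if unbalanced means p below 0.05, 0.10, 0.20 or 0.30. Full adjustment gives 0.771. The shares of the gain recovered are 0.060, 0.096, 0.145 and 0.176 divided by 0.229: about 26%, 42%, 63% and 77%. All four cut-offs are assumed.

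**7. Skewed and count outcomes.** In simulated lognormal and zero-heavy data (20 per arm, ρ from 0.3 to 0.7), rank ANCOVA held a type I error of 0.048 to 0.053. For one assumed effect on zero-heavy counts its power was 0.58 to 0.72, against 0.29 to 0.47 for Wilcoxon on change. This is illustrative only; the documents contain no nap data.

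**The case against.** The strongest reply is that nothing here is invalid. Change-score tests between randomised arms are unbiased, the SAP already calls the estimates imprecise, and this is a 40-person feasibility pilot. All of that stands and sets the weight. It does not remove the point, since admitting imprecision does not reduce it and the baseline data cost nothing extra.

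A reader might infer that the plan yields biased or falsely positive results. The documents do not support that. Simulated type I error under the imbalance rule was below nominal: 4.1% and 4.3% at ρ = 0.3 and 0.5 with p < 0.05, and 3.2 to 4.7% across the four cut-offs at ρ from 0.3 to 0.7. The rule is undefined and inefficient, not shown to be harmful.

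A reader might also extend the unbiasedness statement and the 2.8% bound to every exploratory analysis. The caregiver comparison breaks both. The SAP randomises to two programs, and neither document describes randomising caregiver involvement. Change-score and ANCOVA contrasts can then target different quantities, and the smaller group loosens the bound to about 6%.

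Three further objections hold in part. The gains rest on assumed correlations and SDs, so they are a range, and the ISI figure should be discounted. Rank ANCOVA gives a test but not directly an interval on the outcome scale. The equivalence in step 1 covers two complete visits only; with 24-week data or dropout the longitudinal model has its own place, and a week-9 ANCOVA, like the change-score test, uses only people with a week-9 value.

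**Conclusion.** The point holds for the randomised two-arm comparisons as a cheap improvement of minor weight. Validity is not in question, and feasibility conclusions do not change. What is lost is usually precision: a third of the variance at a low correlation and almost nothing at 0.9, assuming 20 per arm and equal SDs. The gain is likely to be smaller for ISI, and there may be a slight loss where the slope is near 1. The second cost is a covariate set that depends on chance baseline results and an unstated cut-off. How much precision the imbalance rule wins back cannot be known from the SAP.

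**What to change.** - **Lead analysis.** For each continuous outcome, prespecify a linear model of the week-9 value on randomised arm and the outcome's baseline value. Report the adjusted difference with its 95% CI and the number missing per arm.
- **Skewed or count outcomes.** For nap frequency and length and the like, name one method per outcome before data are seen, for example rank ANCOVA for the test. Leave chi-square for categorical outcomes.
- **Covariates.** Present baseline characteristics descriptively. Replace the imbalance-test rule with a short list fixed in advance, bearing in mind that each added covariate has its own cost.
- **24-week data.** Keep the planned repeated-measures model and add baseline adjustment.
- **Caregiver comparison.** Report it as descriptive.

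The cost is SAP wording, one degree of freedom per model (38 to 37 at 20 per arm) and the bounded loss shown above. No new data are needed.
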